### **B.7.2. EFFECTIVENESS ASSESSMENT DEFINITIONS**

Primary Effectiveness Assessment: For subjects who have a successful Trial Phase and receive a permanent implant, the Primary Effectiveness Assessment occurs at the follow up visit 3 months after Device Activation.

### **B.7.3. PRIMARY ENDPOINT**

Pain rating on the 10 cm Visual Analog Scale (VAS) is considered the primary outcome measure. VAS is the most widely used outcome measure in assessing pain due to its documented reliability and validity, ease in administration, and minimal training requirements for the administrator.

The primary effectiveness endpoint is the percentage of implanted subjects who respond to DTM SCS therapy at 3-months after device activation.

An Individual Responder is a subject that reports a decrease in upper limb pain VAS score by at least 50% at 3 months after activation of the permanent SCS system (Device Activation) as compared with Baseline measurement.

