## PROTOCOL SYNOPSIS

Study Title	A Post-Market, Observational Clinical Study to Evaluate the Effects of DTM™ SCS programming in treating Intractable Chronic Upper Limb Pain
Protocol Number	DTM-PROC-2020PM3
Study Device	Intellis™ neurostimulator, a Spinal Cord Stimulation (SCS) device system manufactured and commercialized by Medtronic (Minneapolis, MN)
Study Purpose	The purpose of this observational clinical study is to evaluate the effectiveness and to collect safety data of DTM™ SCS programming on subjects with chronic, unilateral or bilateral upper limb pain.
Study Design	This is a post-market, open-label, prospective, multi-center, observational study evaluating upper limb pain relief with the DTM SCS programming approach. Data at follow-up visits will be compared to baseline assessments collected at the beginning of the study.
Study Size	Up to 90 subjects may be consented and screened in clinical sites in the United States. This would allow approximately 45 subjects to be implanted.
Study Duration	The expected total duration of this study is approximately 26months. Enrollment of subjects is expected to last 20 months. Subjects that have received the permanent implant will be followed up for 12 months after their device has been activated. A subject will likely be committed to the study for about 14 months. This consists of Baseline assessments, up to 10 days of trial stimulation and 12months of treatment following implantation and activation of the device. All current subjects or those who have completed their 6-month visit will be offered to return for an additional 12-month visit. This would increase their commitment to the study to 14 months.
Study Objective	The primary objective of this study is to evaluate the effectiveness of DTM SCS programming as a treatment for reducing intractable chronic pain of the upper limbs.

	
The secondary objectives of this study are to further characterize the effectiveness of DTM SCS programming for the treatment of chronic pain of the upper limb and to collect safety data of DTM SCS programming.

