### **A.3. STUDY SIZE**

Approximately 45 subjects are expected to complete the 3-month endpoint of the study. Up to 90 subjects may be consented to participate at clinical sites in the United States. A sample size estimate is discussed further in section B.5.5 of this Clinical Study Plan.

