#### **B.5.4.1 SAMPLE SIZE RATIONALE**

There is no statistical hypothesis to be evaluated in this study. It is believed that approximately 45 subjects permanently implanted subjects will be sufficient to evaluate the effectiveness and to collect additional safety data of the DTM SCS programming in the target population at the primary endpoint.

Up to 90 subjects will be consented to participate in the eligibility screening process. Those who do not meet all the inclusion criteria and none of the exclusion criteria will be considered screen failures and will not move into the trialing phase. It is estimated that approximately 55 subjects will be trialed. Only subjects with a successful trial phase will be eligible to move into permanent implantation of the device.

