#### **B.6.5. SCS TRIAL PHASE**

Subjects will undergo a Trial Phase with DTM SCS programming. The Trial Phase will last up to 10 days. Percutaneous leads will be placed in the epidural space at a vertebral level based on the subject's pain condition and pain pattern as described in the Physician Implant Manuals. Stimulation will be delivered from an external neurostimulator (ENS).

Anterior-posterior (AP) and lateral X-ray imaging will be done following lead placement at the beginning of the Trial Phase. The subject should flex forward prior to the final AP and lateral X-ray imaging. Additional Imaging may be required if lead migration is suspected throughout the trial.

Stimulation therapy will be as follows:

- Subjects will be given multiple program groups to try. Each DTM SCS program group will have multiple parameters. The stimulation parameters will be within the specifications described in the Intellis™ manuals. Each DTM SCS program group has at least two programs with different pulse rate in the 50 to 1,000 Hz range and each having a maximum pulse width of 1 ms. The subject will progress through each of the program groups until satisfactory pain relief has been reached. The subject will be able to adjust the intensity of the stimulation as deemed needed to obtain pain relief. If sufficient pain relief is not achieved with the initial program group, the subject will be instructed to trial another DTM SCS program group.

Following the standard of care of SCS, adjustments to a program group may be made based on patient feedback following the trialing of a particular program group or set of stimulation parameters. The primary factor for assessing response to a given program group or stimulation parameters is the subject's self-reported pain relief. Adjustments to therapy will be attempted until at least 40% self-reported pain reduction from baseline is achieved or until conclusion of the trial phase (no more than 10 days). Subjects will be assessed for study-related adverse events and medication usage during the duration of the Trial Phase.

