### **B.6.6. END OF TRIAL ASSESSMENT**

At the end of the Trial Phase, subjects will be assessed for pain intensity under optimal therapy parameters. Anterior-posterior (AP) and lateral X-ray imaging may be done at the end of the Trial Phase. The subject will be assessed for study-related adverse events and medication usage.

Subjects who have a "successful Trial Phase" (defined as a 40% or greater pain reduction from Baseline in the upper limbs pain and the subject would like to move forward to the implant phase) will proceed to permanent implantation of a SCS system to evaluate DTM SCS programming. Permanent implantation of the Intellis™ SCS system will be scheduled. A threshold of 40% for the Trial Phase was predetermined as the minimum pain reduction that warrants consideration of a permanent implant and an opportunity to achieve a 50% pain reduction as defined in the Individual Subject Success criterion (see Section B.7.3).

Subjects who did not achieve 40% or greater pain reduction in upper limb and do not receive permanent implantation will exit the study after being followed up for two weeks after removal of the leads to assess study-related adverse events.

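### The only planned responder rate is among implanted subjects, who were selected on early relief from DTM, and no success or responder rate is specified over everyone who starts the DTM trial phase

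*Combined protocol and SAP*

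**What the plan says.** All references are to the combined protocol and SAP.

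- **Therapy in the trial phase (B.6.5).** "Subjects will undergo a Trial Phase with DTM SCS programming". Programming is adjusted until relief reaches at least 40% or the phase ends, at 10 days at most.
- **Route to implant (B.5.4.1, B.6.6).** "Only subjects with a successful trial phase will be eligible to move into permanent implantation of the device". B.6.6 defines success as at least 40% relief from Baseline together with the subject's wish to go on.
- **Route out (B.6.6).** "Subjects who did not achieve 40% or greater pain reduction in upper limb and do not receive permanent implantation will exit the study", after two weeks of adverse event follow-up.
- **Primary endpoint (B.7.3).** "The primary effectiveness endpoint is the percentage of implanted subjects who respond to DTM SCS therapy at 3-months after device activation". A responder has a fall of at least 50% in upper limb VAS from Baseline.
- **Analysis population (B.7.1).** Only one is defined: implanted subjects who complete the study without a major deviation.
- **Other endpoints (B.7.4, B.7.5).** Neither list contains a trial-success proportion or any other responder rate.
- **Planned flow.** "Up to 90 subjects will be consented to participate in the eligibility screening process" and "It is estimated that approximately 55 subjects will be trialed" (both B.5.4.1). The Synopsis adds: "This would allow approximately 45 subjects to be implanted".

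**The concern.** The trial-phase threshold and the primary endpoint use the same therapy, the same symptom and the same reference value, because B.6.3 makes the eligibility pain score the Baseline. A subject who does poorly on DTM in the trial phase is normally not implanted and so cannot count against DTM in the primary rate.

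The Synopsis objective concerns DTM as a treatment for chronic upper limb pain, and B.1 looks ahead to wide use if DTM proves effective. The study has one open-label arm and no hypothesis test, so a descriptive percentage is its main result, and the denominator decides what that percentage means. A clinician considering a DTM trial phase for a patient wants to know how often patients who start one end up with useful relief. The implanted rate alone does not say, and it will be higher than the rate among all who start, unless everyone who starts is implanted or nobody responds.

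**Working it through.** **Inputs**

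- Trialed: about 55 (B.5.4.1).
- Implanted: about 45 (Synopsis, B.5.4.1).
- Completing 3 months: also about 45 (A.3: "Approximately 45 subjects are expected to complete the 3-month endpoint of the study").
- Implanted responder rate: not given in the plan. I assume about 50% to 90%.
- Attrition after implant: not given. I assume 5% to 15%.

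The plan has no hypothesis, power or target precision, so there is no sample-size formula to reproduce. Only the flow can be checked.

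**Step 1: subjects outside the denominator.** 55 − 45 = 10, and 10/55 = 18.2%. The implied trial-to-implant proportion is 45/55 = 81.8%. The plan does not state these figures; they follow from its two approximate ones.

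**Step 2: rate over all trialed.** Let x be the number of 3-month responders, with those not implanted counted as non-responders. Then

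rate over trialed = x/55 = (x/45) × (45/55) = (x/45) × 0.818.

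Exact (Clopper-Pearson) 95% intervals are given for two cases.

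| Responders x | Of 45 implanted | Of 55 trialed | Fall, points |
|---|---|---|---|
| 22 | 48.9% | 40.0% | 8.9 |
| 27 | 60.0% (44.3–74.3) | 49.1% (35.4–62.9) | 10.9 |
| 31 | 68.9% | 56.4% | 12.5 |
| 36 | 80.0% (65.4–90.4) | 65.5% (51.4–77.8) | 14.5 |
| 40 | 88.9% | 72.7% | 16.2 |

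**Step 3: the other meaning of 45.** If 45 is the number completing 3 months, the number implanted is 45/(1 − attrition), rounded up.

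| Assumed attrition | Implanted | Not implanted | Lost after implant |
|---|---|---|---|
| 5% | 45/0.95 → 48 | 55 − 48 = 7 | 48 − 45 = 3 |
| 10% | 45/0.90 = 50 | 55 − 50 = 5 | 50 − 45 = 5 |
| 15% | 45/0.85 → 53 | 55 − 53 = 2 | 53 − 45 = 8 |

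On this reading, fewer subjects are lost at the trial phase. The rest are implanted subjects whom the completer population in B.7.1 leaves out. The total between 55 trialed and 45 analyzed is still 10.

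**Step 4: are the data there?** B.8.1 and Table 1 schedule VAS at the end of the trial phase, and Table 1 has study completion recorded for subjects whose trial phase is not successful. Both added rates can be computed without a new visit or form.

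**The case against.** The strongest reply is that the denominator is openly declared. The Synopsis and B.7.3 say implanted subjects, B.7.2 limits the primary assessment to those with a successful trial phase and an implant, B.4 calls the trial period standard of care, and B.6.6 explains the choice of 40%. All of that stands. This is a choice that limits interpretation, not a contradiction, and it gives no reason to replace the primary endpoint.

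A reader might infer four stronger things that the documents do not support.

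- **That the objective is effectiveness in the enrolled population.** Neither the Synopsis nor B.2 says so. In B.6.2 enrolled means consented, which covers up to 90 people, many of whom would never be trialed.
- **That no planned result includes subjects who leave after the trial phase.** End-of-trial VAS is an effectiveness measure in B.8.1, B.9.2 promises summary statistics for all outcome data, and B.8.3 covers adverse events at all visits. What is missing is narrower: a success or responder rate over trialed subjects, and a population on which to compute it.
- **That the primary rate only shows how many existing responders remain so.** Entry to implant needs 40% relief and response needs 50%. A subject with 40–49% relief in the trial phase is not yet a responder and may become one.
- **That the roughly 10 subjects are mainly DTM failures.** Relief below 40% is the main documented way out, but B.6.6 also requires the wish to proceed and B.6.17 lists other reasons to withdraw. The plan gives no split.

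There is also a fair objection to the supportive rate. It classes someone with good trial-phase relief who declines surgery as a non-responder, and it combines an outcome at 10 days or less with one at 3 months. That is a reason to show the components, not to omit the rate.

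**Conclusion.** The concern holds as a limit on what the main result can show. The primary percentage is conditional on early relief from DTM itself, and the plan specifies nothing over trialed subjects to set beside it.

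On the plan's own flow, the implanted rate is multiplied by about 0.82, a fall of roughly 9 to 16 percentage points over assumed implanted rates of about 50% to 90%. At an assumed 60%, fewer than half of those trialed would be counted as responders.

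These sizes rest on two approximate planning figures, on assumed response rates, and on counting everyone not implanted as a non-responder. The number lost at the trial phase is about 10 if 45 means implanted. It is about 2 to 7 if 45 means 3-month completers and attrition is 5–15%. The point merits a supportive analysis and leaves the primary endpoint as it is.

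**What to change.** Keep the implanted rate as primary. Add to B.7.4:

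- **(a)** the proportion of subjects starting the DTM trial phase whose trial phase is successful;
- **(b)** a supportive 3-month responder rate among all subjects who start the DTM trial phase, counting those not implanted as non-responders.

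Give each an exact 95% confidence interval. Define the all-trialed population in B.7.1. Report both beside the primary rate with the numbers consented, trialed, implanted and assessed at 3 months. Among those not implanted, show separately those with less than 40% relief and those who declined or withdrew. This separation matters for (a) because B.6.1 defines success by relief alone while B.6.6 adds the wish to proceed; the two sections need to be reconciled. Also state whether 45 means implanted or completing 3 months.

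**Cost.** No new data, visits or change in subject management. The supportive figure will be less favourable than the primary one and counts subjects who decline the implant as non-responders. It needs a plan amendment with sponsor and IRB approval under E.6. Revision 3.0 is dated 30JUL2021, about 15 months after the first release, in an open-label study. The added rates should therefore carry the date of their amendment and be labelled supportive.

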### **B.7.4. SECONDARY ENDPOINTS**

The following secondary endpoints will be evaluated:

- Change from Baseline in upper limb pain mean VAS score determined at the 3-month visit after device activation. This is calculated as: Change from Baseline in Upper Extremities Pain VAS = 3-Month Visit Pain VAS – Baseline Pain VAS. A negative result reflects a decrease in Pain VAS score, while a positive result reflects an increase in Pain VAS score.
- Change from Baseline in extend of disability as measured by mean Pain Disability Index (PDI), evaluated at 3 months after device activation.
- Frequency of treatment emergent adverse events.

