The implanted INS will be activated within 14 days after surgical procedure and SCS therapy will be evaluated for the next 12 months. Activation of the device marks the initial time point for effectiveness evaluation of the study therapy after implantation. Assessments of pain intensity, use of medication and study-related adverse events will be made through the 12 month following Device Activation. Additionally, a 3, 6 and 12months after Device Activation, subjects will also be assessed for extent of disability, Patient Global Impression of Change, subject satisfaction and paresthesia. All current subjects or those who have completed their 6-month visit will be offered to return for an additional 12-month visit. This would increase their commitment to the study to 14 months. Figure 1 summarizes the sequence of study-related assessments, procedures, and activities.

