#### **B.6.4. BASELINE**

A subject that is eligible to continue into the trial phase according to the inclusion and exclusion criteria will be requested to fill out standard questionnaires that will assess extent of disability and use of medications. The medical and surgical history of the subject will also be collected. At this visit and subsequent visits, the subject will be assessed for study-related adverse events, medication usage and will be reminded to not increase pain medications from baseline through the 3-Month Visit. Pre-operative assessments will follow the standard of care for SCS therapy and be determined by the site Investigator.

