### **B.6.12. 3 MONTHS AFTER DEVICE ACTIVATION ( $\pm$ 21 DAYS)**

Subjects will visit the study site where they will be assessed for pain, other pain (if applicable), extent of disability, Patient Global Impression of Change, and subject satisfaction. Paresthesia generated by the stimulator will be assessed. Programming adjustments may be made, as needed. Anterior-posterior (AP) and lateral X-ray imaging will be done. Subjects will also be assessed for possible study-related adverse events and medication usage. If there are no ongoing study-related adverse events, the subject will complete the study at this visit. In situations where there is an ongoing study-related adverse event, subjects will be followed until resolution of that adverse event or determination that the subject's condition is stable, at which point the Study Completion CRF should be completed.

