### **B.6.13. 6 MONTHS AFTER DEVICE ACTIVATION ( $\pm$ 31 DAYS)**

. The 6 Months visit will consist of the same assessments as the 3-month visit except the anterior-posterior (AP) and lateral X-ray imaging is optional. Subjects will visit the study site where they will be assessed for pain, extent of disability, quality of life, Patient Global

Impression of Change, and subject satisfaction. Paresthesia generated by the stimulator will be assessed. Programming adjustments may be made, as needed. Subjects will also be assessed for possible adverse events and medication usage. In situations where there is an ongoing study related adverse event, subjects will be followed until resolution of that adverse event or determination that the subject's condition is stable.

However, all subjects who remain implanted at the time of Study Completion will be offered to return for an additional visit 12-months after device activation.

Following the last scheduled study visit, subjects will be followed by their pain physician at regular intervals, as dictated by standard of care at each site, in order to facilitate pain management, stimulation adjustments, possible revisions and/or replacements of neurostimulation components. Any additional non-study related monitoring of the subject will be the responsibility of the subject's personal physician, as dictated by reasonable medical care.

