## **B.8. EVALUATION CRITERIA**

### **B.8.1. EFFECTIVENESS**

Results of the tests and standard questionnaires will be recorded in Case Report Forms at Baseline and during follow-up visits. Changes from Baseline will be calculated.

Effectiveness will be measured for each subject using the following tests:

- Pain
- Visual Analog Scale (VAS, 10 cm) at Baseline, End of Trial Phase, Months 1, 3, 6 and12 monthsDisability
  - Pain Disability Questionnaire at 3, 6 and 12 months
- Impression of Change in Quality of Life
  - Patient Global Impression of Change at 3, 6 and 12 months
- Satisfaction with Therapy
  - Subject Satisfaction Questionnaire at 3, 6 and 12 months
- Paresthesia generated by the stimulation
  - Paresthesia Questionnaire at 3, 6 and 12 months

Study personnel will be appropriately trained for administration of each test.

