## **B.9. DATA COLLECTION AND ANALYSIS**

### **B.9.1. DATA COLLECTION**

Study data will be collected using paper CRFs. Each data field is expected to have a verifiable source document. Subject confidentiality will be maintained, and each subject will be identified by the assigned study subject number. Subject names will not be published.

Data collection is summarized in Table 1.

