**Table 1. Schedule of Study Activities**

Activity	Pre-Trial Phase		Trial Phase		Permanent Phase					12 months visit (±31 days after activation)
	Enrollment	Baseline	Start Trial Phase	End Trial Phase (up to 10 days after trial starts)	Permanent Implant (up to 60 days after end of trial)	Device Activation (0-14 days after implant)	1-month visit (±15 days after activation)	3 months visit (±21 days after activation)	6 months visit (±31 days after activation)	
Informed Consent	X									X b)
Pain Intensity Evaluation (VAS)	X			X			X	X	X	X
Medication Use	X	X	X	X	X	X	X	X	X	X
Medical/Surgical History	X	X								
Eligibility Criteria Evaluation	X									
Pain Disability Questionnaire		X							X	X
AP/Lateral x-ray imaging			X	[X]	X	[X]	[X]	X	[X]	[X]
Paresthesia Questionnaire								X	X	X
Patient Global Impression of Change								X	X	X
Subject Satisfaction								X	X	X
Adverse Event Monitoring		X	X	X	X	X	X	X	X	X
Device Programming			X			X	[X]	[X]	[X]	[X]
Device Programming Log				[X]			[X]	[X]	[X]	[X]
Study Completion				X a)				[X] c	[X] c	X c

[X] Optional activity.

a) For subjects that do not have a successful Trial Phase.

b) Some subjects may need to be reconsented to complete these visits.

c) Some subjects were originally consented to complete the study at the 3 or 6 month visit and may not consent for additional visit.

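### Table 1 leaves the disability questionnaire unmarked at 3 months, the visit at which the secondary disability endpoint is defined

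*Combined protocol and SAP*

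**What the plan says.** B.7.4 lists three secondary endpoints: change in upper limb pain VAS at 3 months, adverse event frequency, and "Change from Baseline in extend of disability as measured by mean Pain Disability Index (PDI), evaluated at 3 months after device activation".

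Three other sections call for disability at the 3-month visit:

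- B.6.1: "3, 6 and 12months after Device Activation, subjects will also be assessed for extent of disability".
- B.6.12, which describes the 3-month visit, has subjects "assessed for pain, other pain (if applicable), extent of disability, Patient Global Impression of Change".
- B.8.1 gives the form and its follow-up times: "Pain Disability Questionnaire at 3, 6 and 12 months".

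B.6.13 adds indirect support: "The 6 Months visit will consist of the same assessments as the 3-month visit except the anterior-posterior (AP) and lateral X-ray imaging is optional". It then lists disability among the 6-month assessments.

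For the starting value, B.6.4 has eligible subjects complete "standard questionnaires that will assess extent of disability and use of medications".

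B.9.1 states: "Data collection is summarized in Table 1". In that table the row "Pain Disability Questionnaire" is marked at Baseline, 6 months and 12 months. The 3-month cell is empty.

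**The concern.** A change from baseline to 3 months needs a score at both times. Table 1 secures the first and not the second. It is the only visit-by-visit grid of forms in the document, so it is what a coordinator would naturally use to assemble a visit packet. B.6.12 asks for disability at that visit but names no form, and so does not by itself send the reader to the questionnaire.

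Two features of the plan add to the exposure. B.6.15 allows visits to be done remotely, with the required questionnaires sent out or read over the telephone; a packet built from Table 1 would lack this form. Also, B.6.12 still has subjects without an ongoing study-related adverse event finishing the study at 3 months, and note c to Table 1 recognises that some subjects consented only to 3 or 6 months. If Table 1 were followed, a subject who left at 3 months would contribute no disability score after implantation.

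For subjects who continue, the 6-month score is a different quantity from the one B.7.4 defines. A 3-month score not obtained in or near its window of ±21 days cannot be reconstructed from later visits.

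**Working it through.** No sample size, power or error rate is involved. B.9.2 states that there are no formal hypotheses. The check is a comparison of the schedule with the text.

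**Step 1: read the row.** Table 1 has ten visit columns: Enrollment, Baseline, Start Trial, End Trial, Implant, Activation, and 1, 3, 6 and 12 months. Each of its 14 rows yields ten cells. The four assessments that B.6.1 places at 3, 6 and 12 months are marked as follows:

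| Row in Table 1 | Baseline | 3 months | 6 months | 12 months |
|---|---|---|---|---|
| Disability | X | blank | X | X |
| Paresthesia | blank | X | X | X |
| Global impression of change | blank | X | X | X |
| Satisfaction | blank | X | X | X |

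Three of the four are marked at 3 months. Disability is the exception.

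**Step 2: rule out a column shift.** The disability row has its full ten cells, with marks in columns 2, 9 and 10. The other three rows are marked in columns 8, 9 and 10. The columns are aligned, and the empty cell is column 8, the 3-month visit. This excludes a shift. It does not exclude a single mark dropped in conversion, which would leave the same ten cells.

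**Step 3: compare the 3-month and 6-month columns.** Twelve of the 14 rows agree. Three of those (consent, medical history, eligibility) are blank in both columns, so 12 − 3 = 9 agreements carry information. Two rows differ:

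- X-ray: required at 3 months and optional at 6, as B.6.13 says.
- Disability: blank at 3 months and marked at 6, with no explanation anywhere.

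**Step 4: set the sources side by side.**

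| Source | Disability at 3 months? |
|---|---|
| B.6.1 | Yes |
| B.6.12 | Yes |
| B.7.4 | Yes, as a secondary endpoint |
| B.8.1 | Yes, questionnaire named |
| Table 1 | No |

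Four sections agree and the table stands alone. Baseline is not in doubt: B.6.4, the opening of B.8.1 and Table 1 all provide for it.

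**The case against.** The strongest objection is about certainty. The point rests on one empty cell in a table extracted from PDF, and the alignment check cannot detect a lost mark. That stands as a caveat: the contradiction is certain in the text available, and the source file should be checked before the table is edited.

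The second objection is that the plan already guards against the harm. B.6.12 requires the assessment, and B.8.1 supplies the form and the month. B.6.15 allows questionnaires by telephone, email or post, and asks only that windows be kept as far as possible. E.1.2 has monitors review missing results and the investigator try to obtain them. These provisions lower the chance of permanent loss. They do not correct the schedule, and a monitor who checks completeness against Table 1 would see nothing missing.

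Third, the B.6.13 sentence is weaker support than it looks. Its own list adds quality of life and leaves out other pain, so the two visits are not described identically. This is fair, but the finding does not depend on B.6.13, because four other sections state 3 months directly.

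Fourth, the current document is Revision 3.0, dated 30 July 2021, and the first revision dates from 20 April 2020. Some 3-month visits may already have taken place under earlier schedules that are not available here. Correcting the cell can only help visits still to come, and their number is unknown. This limits the benefit of the edit and strengthens the case for checking which form the sites actually used.

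**Conclusion.** The inconsistency is real. As written, Table 1 omits the disability questionnaire at the only follow-up visit that B.7.4 uses for the disability endpoint, against four sections that require it.

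Of the three secondary endpoints, two concern effectiveness (VAS change and disability change), and one of those two is exposed. The extent of any data loss cannot be estimated from the documents, because the case report forms and worksheets are not supplied and the visit text still asks for the assessment. The endpoint is descriptive and the primary endpoint is unaffected. The point should be corrected, but it does not threaten the study as a whole.

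The conclusion assumes that the blank cell is in the source document and was not created by conversion.

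**What to change.** 1. Check the 3-month cell of the disability row in the source file. If it is blank there, mark it.
2. Confirm that the 3-month case report form and visit worksheet include the disability questionnaire, and establish whether 3-month visits already completed collected it.
3. In the same edit, use one instrument name. B.7.4 names the Pain Disability Index, while B.8.1 and Table 1 name a Pain Disability Questionnaire, and the document never says they are the same. The name should match the form in Appendix B. Adding Baseline to the disability line in B.8.1 would complete it. Both are minor, and the main point does not rest on them.

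The cost is one table cell, some wording and a check of the forms. Subjects carry no added burden, because B.6.1, B.6.12 and B.8.1 already require the 3-month assessment.
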